6.2 Identification of subjects

Subjects with a diagnosis of standard HER-2/neu-positive IBC or HER-2 2+ but FISH negative with Stage IIIA \geq N2, or have recurrent HER-2 positive metastatic breast cancer rendered NED by any means that have completed chemotherapy and/or trastuzumab will be recruited from the Rowan Breast Center. Up to 18 patients will be enrolled in this Pilot Phase I trial. No exceptions to eligibility will be made.

Fifteen subjects were enrolled at Rowan Breast Center.

Study Schema: Adjuvant HER2+

Inclusion Criteria

- 1. Women ≥ 18 years.
- Subjects with Invasive Breast Cancer at least Stage IIIA ≥ N2 (>4 positive nodes) or have recurrent metastatic breast cancer rendered NED by any means that are classic HER-2 3+ 10%, 2+ IHC and FISH positive or HER-2 2+ FISH negative that have completed chemotherapy and/or trastuzumab and have no evidence of disease.

Version v2 03/01/2017

Pilot Phase I HER-2 Pulsed DC Vaccine to Prevent Recurrence for Patients with HER-2 Driven High Risk Invasive Breast Cancer

- 3. Patients deemed to require anti-estrogen therapy for treatment of their breast cancer can continue anti-estrogen therapy during vaccinations
- 4. Women of childbearing age with a negative pregnancy test documented prior to enrollment.
- 5. Patients with ECOG Performance Status Score of 0 or 1 (Appendix D).

- 6. Women of childbearing potential must agree to use a medically acceptable form of birth control (medically accepted methods: birth control pills, condoms and spermicidal lubricants, intrauterine device, and diaphragm) during their participation in the study.
- 7. Subjects who have voluntarily signed a written Informed Consent in accordance with institutional policies after its contents have been fully explained to them.

Exclusion Criteria

- 1. Pregnant or lactating females.
- 2. Subjects with positive HIV or hepatitis C at baseline
- 3. Subjects with coagulopathies, including thrombocytopenia with platelet count <75,000, INR > 1.5 and partial thromboplastin time > 50 sec
- 4. Subjects with major cardiac illness MUGA < 50% EF.
- 5. Subjects with pre-existing medical illnesses or medications which might interfere with the study as determined by PI.

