6.3 Pre-enrollment screening

- A. Tumor Characteristics
 - 1. A core biopsy or excisional biopsy demonstrating IBC.
 - 2. A standard clinical HER-2/neu immunohistochemical stain and FISH test will be performed using the Hercept test (Dako) on specimens obtained by core biopsy material or resected tumor.
 - 3. A standard clinical ER, PR test.
- B. Baseline patient evaluation
 - 1. All subjects will have a baseline history and physical exam.
 - 2. Laboratory work-up will consist of:
 - a) CBC w/ differential
 - b) PT/PTT
 - c) electrolytes-Na/K/Cl/CO₂/BUN/Cr/glucose
 - d) liver function tests
 - e) urinalysis
 - f) Beta-HCG serum (for all pre and perimenopausal women)
 - g) EKG
 - h) HLA typing (to be obtained as part of study)
 - i) MUGA or Echocardiogram (Must have 50% EF)
 - j) Blood for immune analysis (6 tubes)
 - 3. Baseline radiologic evaluation
 - a) Mammogram up to six months prior to consenting to participate in the study will be acceptable. (Unilateral or bilateral if bilateral mastectomies mammogram not needed)

- b) CT scans of the chest abdomen and pelvis or PET/CT within 60 days of enrollment
- C. Performance of the Pre-screening tests

All of the pre-screening tests will be obtained by the patient prior to first treatment.

1. Histopathologic Testing of Tumor

Subjects will have undergone core or resection of primary tumor prior to enrollment in this protocol to confirm diagnosis of IBC. The Hercept (Dako) antibody will be used to analyze the expression of HER-2/neu on the IBC. Conventional HER-2 3+ 10% of the cells will be considered classic HER-2 positive or 2+ with FISH amplification 2 fold increase in FISH amplicons. For HER-2 2+ FISH negative, ten percent of the cells staining at least 2+ will be considered positive for HER-2/neu expression.

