6.5 Post-Vaccine Procedures

A. In vitro Immunologic testing

Subjects will have 5mL of peripheral whole blood drawn at multiple time points during the vaccine schedule (pre vaccine, post six vaccines, pre booster 1, pre booster 2, pre booster 3, and completion of all vaccinations) to monitor immunologic responses to the administered vaccines. Subjects will also have the option to undergo additional leukapheresis (10-15 liters) at the completion of the 6 vaccines or completion of the three boosters to obtain T lymphocyte population for additional immunologic analysis. The leukapheresis will be performed in the pheresis facilities at the University of Pennsylvania by certified personnel or at Moffitt Cancer Center, if needed. Attempts will first be made to obtain peripheral access for the pheresis protocol. Subjects will be pheresed 15-20 liters whole blood on a Gambro Spectra or equivalent apparatus. We expect to be able to generate $1-5 \times 10^{10}$ PBMC.

B. Post vaccine laboratory studies

In addition to the blood which will be drawn for the above analyses, an extra tube of serum will be drawn to test the subject's anti-HER-2/neu response. After boost vaccines additional 5 tubes of whole blood will be obtained for immune analysis. These results will be compared with the immune response results that will have been obtained prior to vaccination. An alternative post vaccine leukapheresis can be performed as alternative to blood draws.

- 1. After receiving their vaccines and prior to receiving boost vaccine series, subject will have the following completed:
 - a) CBC w/ differential
 - b) PT/PTT
 - c) electrolytes-Na/K/Cl/CO₂/BUN/Cr/glucose
 - d) liver function tests
 - e) urinalysis
 - f) MUGA or Echocardiogram (Compare to first study)

In addition to the blood drawn for the above analyses, 5 tubes of whole blood will be obtained for immune analysis and tube of serum will be drawn to test subjects anti-HER-2/neu response. These results will be compared with the immune response results that will have been obtained prior to vaccination.

In the event of abnormal symptoms, laboratory monitoring may be done earlier. The laboratory studies and intervals at which they are done will be determined by the PI on a case by case basis.

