If significant decline in EF was evident in pre/post vaccine MUGA scan or ECHO, another MUGA scan or ECHO may be performed 1 month post-vaccine, as determined by the PI. Subjects will be closely monitored by the PI, who will determine the need for additional MUGA scan(s) during the 6 month post-vaccine monitoring period on a case by case basis.

C. Long-term Follow-up

After completing the 6 month post-vaccine monitoring period, all subjects will be seen yearly. Mammograms will be obtained at yearly visits if patients have remaining breasts. For Version v2 03/01/2017 30 Pilot Phase I HER-2 Pulsed DC Vaccine to Prevent Recurrence for Patients with HER-2 Driven High Risk Invasive Breast Cancer mastectomy subjects a yearly mammogram of the contralateral breast. This will continue for 5 years.

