6.9 Statistical Considerations

6.9.1 Design. A single arm phase I trial of HER-2 pulsed DC1 vaccine in subjects with high risk HER-2^{pos} breast cancer with residual disease after neoadjuvant therapy. Subjects will receive 6 weekly DC1 vaccinations and may then be eligible to receive up to 3 boost vaccinations given every 3 months. This study will enroll 18 evaluable subjects. Evaluable implies that a subject received all 6 weekly vaccinations and underwent leukapheresis after the vaccinations for immune response evaluation. Subjects will be followed for 30 days after their *final* vaccination.

6.9.2 Objectives. The primary objectives are to determine feasibility and safety. The secondary objectives are to evaluate immunogenicity and anti-HER2 immunity.

6.9.3 Endpoints. Feasibility is defined as a subject's ability and willingness to complete the treatment regimen (6 weekly vaccinations). Safety is established by grading the observed toxicities using CTC Version 3.0. Cardiac toxicity due to trastuzumab will be monitored 2 weeks after the sixth weekly vaccination (week 8) and at EOS and scored separately from vaccinerelated toxicity. Cardiac toxicity is defined as either asymptomatic change in MUGA (i.e., >20% decline in EF by repeat echo or EF <50%) or symptomatic EF drop or heart failure. Doselimiting toxicity (DLT) due to vaccination is defined as: Grade 2 allergic reaction/generalized urticaria, > Grade 3 allergic reaction/other, > Grade 2 autoimmune reaction, > Grade 2 cardiac toxicity or as specified above, > Grade 3 hematologic and non-hematologic toxicity (except fever) and > Grade 2 toxicity due to leukapheresis. DLT rate will be defined by the weekly vaccination schedule. Toxicities will be scored separately for the maintenance boost schedule. Immunogenicity is evaluated with descriptive statistics and box plots for multiple CD4+ and CD8+ T cell metrics obtained at baseline, 2 weeks after the sixth weekly vaccination (week 8) and after each maintenance boost, as show in the table below. Immune response (IR) is defined as >2 fold increase relative to baseline. Anti-HER2 response will be a quantitated by dilution studies. Long-term anti-HER2 immunity will be assessed at follow-up visits (e.g., q 6 months).

Immune Parameter	Assay Method	Fold change	Response (>2 fold ↑)
Peptide specific reactivities	Tetramer	~	\checkmark
CD8+ T cell activation or tumor recognition	cytokine release	~	\checkmark

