CD4+ T cell activation	ELISPOT	~	\checkmark
Overall immune response	(response to any of a	above)	

6.9.4 Monitoring Unacceptable Toxicity. Early termination rules for asymptomatic and symptomatic cardiac toxicity and vaccine-related dose-limiting toxicity have been defined for monitoring purposes. Toxicity data will likely be reviewed after groups of 3 women have been treated. Enrollment will be terminated if data indicate that the rate of 1) asymptomatic cardiac toxicity >20%, 2) symptomatic cardiac toxicity/heart failure >5% or 3) vaccine-related DLT rate >25%. For cardiac toxicity, we assume an uninformative beta (1, 1) prior and for vaccine-related DLT we assume a modestly informative beta (1, 3) prior since safety of our DC1 vaccine has been established in >50 women treated on our DCIS trials. Given the prior and the observed data, the Bayesian posterior probability that the toxicity rate exceeds the specified rate, is calculated. If the numbers of subjects with toxicity equals or exceeds the numbers (in shaded rows) in the table below, then it is likely that the toxicity rate is unacceptable, as noted by Bayesian posterior probabilities.

Bayesian Early Termination Rules for Cardiac Toxicity Rate							
Subjects treated	3	6	9	12			
Subjects with asymptomatic cardiac toxicity	1	2	3	4			
Bayesian Posterior Prob[tox rate >20%]	0.82	0.85	0.88	0.90			
Subjects with symptomatic cardiac toxicity/heart failure	1	1	1	1			
Bayesian Posterior Prob[tox rate >5%]	>0.9	>0.9	0.91	0.86			

Subjects with vaccine-related DLT	2	3	4	5
Bayesian Posterior Prob[DLT rate >25%]	0.83	0.83	0.84	0.85
Action	Terminat	te accrual	, re-evalu	ate trial

6.9.5 Statistical Analyses and End of Trial Decision-making. Feasibility. A narrative of reasons why subjects could not complete treatment will be written. Safety. All graded toxicities will be tabled and described by frequency and percentage. Attribution to DC1 vaccine or trastuzumab will be assigned, if possible. All cardiac toxicities will be reported in detail. Toxicities observed during weekly vaccination will be tabled separately from toxicities observed during maintenance boosts. **Immunogenicity**. Immunogenicity will be evaluated by descriptive statistics, plots of pre- and post-treatment values and fold changes. Immune response rate and 95% exact confidence interval will be calculated. Anti-HER2 response will be quantitated as EOS/baseline fold change in dilution studies.

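### The asymptomatic cardiac toxicity endpoint does not fix the EF method within a subject, or say whether the 20% decline is in EF points or percent of baseline

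*Combined protocol and SAP*

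**What the plan says.** Section 6.9.3 gives the asymptomatic form of cardiac toxicity as a change in MUGA, meaning a more than 20% "decline in EF by repeat echo or EF <50"%. Two methods are named for one within-subject change: the change is in MUGA, and the evidence for it is an echo.

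The rest of the protocol does not settle which method applies:

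- Baseline, section 6.3.B: "MUGA or Echocardiogram (Must have 50% EF").
- After the induction vaccines, section 6.5.B: "MUGA or Echocardiogram (Compare to first study").
- After a significant decline, section 6.5.B: "another MUGA scan or ECHO may be performed 1 month post-vaccine, as determined by the PI".
- Exclusion criterion 4, section 6.2: "Subjects with major cardiac illness MUGA < 50% EF"%, with echo not named.
- Appendix 1: a row labelled LVEF. Neither the row nor its footnote names a method.

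The definition is used in three places. Section 6.9.4 monitors the asymptomatic rate against 20%, with boundaries of 1 in 3, 2 in 6, 3 in 9 and 4 in 12 subjects, under this prior: "For cardiac toxicity, we assume an uninformative beta (1, 1) prior". The DLT list in 6.9.3 includes "Grade 2 cardiac toxicity or as specified above". Section 6.9.5 calls for all cardiac toxicities to be reported in detail.

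**The concern.** The decline limb of the endpoint is a difference between two readings on the same woman. If one reading is by MUGA and the other by echo, the difference contains the disagreement between methods as well as any change in her heart. Depending on its direction, that disagreement can produce an event where nothing changed or mask a real fall. Someone who follows the protocol to the letter may make this comparison without any deviation.

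Separately, the size of the fall that counts is not defined. Two people applying 6.9.3 to the same pair of readings could classify the subject differently and both be within the text.

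Safety is a primary objective, and the monitoring rule works on small counts, so the status of a single subject can decide whether a boundary is met.

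**Working it through.** **1. The plan's own figures.** The 6.9.4 posterior is P(rate > 0.20) under Beta(1 + x, 1 + n − x), for x events in n subjects. For 1 in 3 this is Beta(2, 3): 0.8⁴ + 4 × 0.2 × 0.8³ = 0.4096 + 0.4096 = 0.819. All four stated values reproduce. The last column shows the posterior with one event fewer.

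| Subjects | Boundary | Stated | Recomputed | One event fewer |
|---|---|---|---|---|
| 3 | 1 | 0.82 | 0.819 | 0.410 (0/3) |
| 6 | 2 | 0.85 | 0.852 | 0.577 (1/6) |
| 9 | 3 | 0.88 | 0.879 | 0.678 (2/9) |
| 12 | 4 | 0.90 | 0.901 | 0.747 (3/12) |

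The arithmetic of the rule is sound. The last column shows what rests on correct classification: at any boundary, one subject is the difference between meeting the rule and not meeting it.

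**2. Points or percent.** Let b be the baseline EF. With the below-50% limb included, a follow-up reading is an event when it is below:

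- percent of baseline: the larger of 0.8b and 50;
- EF points: the larger of b − 20 and 50.

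The decline limb adds something beyond the 50% limb only if 0.8b > 50, so b > 62.5 (percent), or if b − 20 > 50, so b > 70 (points).

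| Baseline | Event below (percent) | Event below (points) | Readings classified differently |
|---|---|---|---|
| 55 | 50 | 50 | none |
| 60 | 50 | 50 | none |
| 65 | 52 | 50 | 50 to under 52 |
| 70 | 56 | 50 | 50 to under 56 |
| 75 | 60 | 55 | 55 to under 60 |

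Example: 65 to 51 is a fall of 14 points, and 14/65 = 21.5%. It is an event on the percent reading and not on the points reading. This step needs no outside figure.

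**3. A change of method.** The documents give no offset or error between MUGA and echo, so the following only illustrates direction. Suppose true EF is unchanged and the follow-up method reads d points lower than the baseline method.

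- Baseline 65, percent reading: an event if d > 65 − 52 = 13.
- Baseline 65, points reading: an event if d > 65 − 50 = 15, through the 50% limb.
- Baseline 52, either reading: an event if d > 52 − 50 = 2. Entry at 50% permits such a subject.

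The error can also run the other way. On the percent reading, take a subject who starts at 65 and whose follow-up by the baseline method would be 51. If the other method reads one point higher, it gives 52. Then 13/65 = 20.0%, which is not above 20%, and the event is lost.

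**4. Which limb depends on the baseline method.** The decline limb depends on it directly. The 50% limb is a fixed cut on one follow-up reading, so its error comes from the follow-up method. Baseline method matters there only because the value that admitted the subject may have been read by a different technique. Matching methods therefore repairs the decline limb fully and the 50% limb only in part.

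**The case against.** Much of the case against stands, and it limits the point.

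**A large false-stop probability.** A reader might infer that switching methods makes a false stop likely and try to put a percentage on it. The documents do not support this. They give no between-method error. A calculation on the 50% limb alone would be comparing follow-up methods, not matched with mismatched pairs. Applying it to three subjects would also require all three to switch, with the offset always downward.

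**One subject ends the trial.** A reader might also infer that a single switched reading stops accrual. That is true only at the look after three subjects; later looks need two, three or four events. Sections 2.0 and 6.2 record fifteen subjects already enrolled, and the table ends at twelve, so the first look has probably passed. The stated action also includes re-evaluating the trial, which could uncover a measurement artefact, although only after accrual has stopped.

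**Transfers between centres.** Section 2.0 expects about four subjects at the second centre. Nothing says that the two centres use different methods, so a transfer is an occasion for a switch and not evidence of one.

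**Earlier experience.** Section 5.3 reports asymptomatic declines in fewer than 10% of patients, all staying above 50%. Section 6.7.A reports fewer than 8% in the first trial, all in the normal range. This is the only EF evidence in the documents and is reassuring. It does not say whether methods were matched, and 5.3 notes that those patients had not just had chemotherapy or trastuzumab.

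**Existing safeguards.** The repeat echo in 6.9.3 could be read as a confirmatory scan, 6.5.B asks for comparison with the first study, and 6.9.5 asks for detailed reporting. None of these requires the baseline method or defines the percentage.

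**Conclusion.** The point holds as a defect in the endpoint definition, not in the stopping-rule arithmetic. Two gaps are established from the text alone: no section ties a subject's follow-up EF to her baseline method, and the 20% decline has two readings that disagree for some follow-up values at every baseline above 62.5%. Both affect a primary safety result. They carry into the 6.9.4 counts, into the detailed cardiac report and, on the wording of 6.9.3, into the DLT count.

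The size of the method effect cannot be stated, because it depends on how many subjects switch and on the disagreement between methods, and the documents give neither. The definition still matters with fifteen subjects enrolled, since it governs classification for remaining and boosted subjects and for the final report. The change is worth making because it costs little. The text does not show that the trial has stopped, or would stop, in error.

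**What to change.** - In 6.3.B, 6.5.B, 6.9.3 and the LVEF row of Appendix 1, require each subject's follow-up EF to be measured by the same method as her baseline.
- In 6.9.3, replace 'by repeat echo' with 'by the baseline method'.
- In 6.9.3, state whether the 20% is EF points or percent of baseline.
- If a cross-method value does occur, count it in the 6.9.4 table as observed and flag it in the report. Do not withhold it pending a repeat scan: that would delay a possible true event in a safety rule and add a procedure.

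The cost is a short text amendment and occasional scheduling inconvenience, mainly for subjects who change centre. No additional scans are needed.

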Toxicity will be graded according to the NCI-CTCAE version 4.02

C. Toxicity Definition for Leukapheresis

Grade 1: Requirement for oral calcium supplementation either during or just after procedure. Severe bruising requiring treatment such as warm compresses or anti-inflammatory medication for a brief 1 week duration.

Grade 2: Prolonged requirement for calcium administration greater than 24 hours, infection at the intravenous site requiring treatment or intervention with antibiotics or surgery.

Grade 3: Alteration in vital signs such as severe hypotension requiring hospitalization, hospitalization secondary to infection.

D. Dose Limiting Toxicity (DLT)

Since the agent being administered is a biologic agent prepared from the subjects own cells as opposed to a single drug we will lump the toxicity together as that caused by the process of preparation of the DC vaccine. A subject that develops any grade 3 or greater toxicity per the NIH Cancer Therapy Evaluation Program Common Toxicity Criteria version 4.03 except for fever greater than 40° C for <12 hours will be taken off protocol. A continuous monitoring rule for

dose-limiting toxicity will be followed during the trial, as described in section 6.11 Statistical Considerations.

Grade 2 allergic reaction: generalized urticaria Greater than or equal Grade 3 allergic reaction Greater than or equal Grade 2 autoimmune reaction Greater than or equal Grade 3 cardiac toxicity Any Greater than or equal Grade 3 hematologic and non-hematologic toxicity. Greater than or equal Grade 2 toxicity for leukapheresis

E. Adverse Events

Adverse events will be graded according to NCI Common Toxicity Criteria (version 4.03 seehttps://evs.nci.nih.gov/ftp1/CTCAE/About.html. A copy is enclosed in the Appendix.

1. Adverse Event Reporting

All adverse events will whether or not associated with the study agents be recorded on the CRF. Adverse Events will be reported to the IRB, Data Safety and Monitoring Committee (DSMC), Moffitt Cancer Center Protocol Monitoring Committee (PMC);Safety Monitoring Committee, GCRC, FDA, and NIH. The information collected includes:

•The time of onset of any new adverse event or worsening of a previous adverse event

- •The specific type of adverse reaction in standard medical terminology
- •The duration of the adverse event
- •The grade of the adverse event
- •The attribution of the adverse event to the study reagents

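### Sections 6.7 D and 6.9.3 define DLT differently without saying which governs, and the cardiac checks that 6.9.3 requires are not fixed in the assessment schedule

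*Combined protocol and SAP*

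**What the plan says.** **DLT in 6.9.3 (Endpoints).** After urticaria, other allergic reactions and autoimmune reactions, the list continues with "> Grade 2 cardiac toxicity or as specified above, > Grade 3 hematologic and non-hematologic toxicity (except fever") and ends with leukapheresis toxicity. The words pointing back bring in the cardiac definition given just before: an asymptomatic EF fall of more than 20%, an EF below 50%, a symptomatic EF drop, or heart failure. The same section scores cardiac toxicity due to trastuzumab apart from vaccine-related toxicity.

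**DLT in 6.7 D.** The list there has "Greater than or equal Grade 3 cardiac toxicity" and "Any Greater than or equal Grade 3 hematologic and non-hematologic toxicity". It gives no EF criterion. Fever appears only in the preceding sentence on removing a subject, where any grade 3 or higher toxicity "except for fever greater than 40° C for <12 hours will be taken off protocol".

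**Link between the two.** Section 6.7 D says that a continuous monitoring rule for "dose-limiting toxicity will be followed during the trial, as described in section 6.11 Statistical Considerations". There is no section 6.11; Statistical Considerations is section 6.9.

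**Grading.** In 6.7 B: "Toxicity will be graded according to the NCI-CTCAE version 4.02". Sections 6.7 D and 6.7 E cite version 4.03. In 6.9.3: "Safety is established by grading the observed toxicities using CTC Version 3.0".

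**Cardiac schedule.** In 6.9.3, cardiac toxicity "will be monitored 2 weeks after the sixth weekly vaccination (week 8) and at EOS". Section 6.5 B asks for one MUGA or echocardiogram after induction and before the boosts, with no week given. Appendix 1 marks LVEF at Baseline and Booster 1 only. Its EOT column carries only AE, and footnote 4 leaves further LVEF to case-by-case judgement.

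**The concern.** Safety is a primary objective. The DLT count feeds the DLT row of the stopping table in 6.9.4 and the reported DLT rate. It also feeds the example rule of 3 or more in 15 in 6.9.6, if the unacceptable toxicity named there means DLT. Two people applying different sections could score the same subject differently, and one subject separates 2 of 15 from 3 of 15.

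The schedule gap bears on the cardiac safety endpoint. Sections 6.7 A and 7.0 say that the vaccine has not been given before to people treated with Herceptin, so cardiac safety is a new question here. A site that follows Appendix 1 would take the post-induction LVEF about 3 months after vaccine 6 and would have no EOS LVEF unless the PI asked for one. Asymptomatic EF loss after the boosts would then be found only in subjects chosen for a scan.

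**Working it through.** **1. The lists side by side, reading the > in 6.9.3 as at least.**

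| Item | 6.7 D | 6.9.3 |
|---|---|---|
| Cardiac | grade ≥3 | grade ≥2, or the EF criteria |
| Hematologic and non-hematologic | grade ≥3 | grade ≥3, all fever exempt |
| Fever | exempt only if above 40 °C for under 12 h, in the off-protocol sentence | exempt |
| Other allergic; autoimmune; leukapheresis | ≥3; ≥2; ≥2 | ≥3; ≥2; ≥2 |
| Grading | CTCAE 4.02 / 4.03 | CTC 3.0 |

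The differences are the cardiac item, fever and the grading version.

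**2. The plan's own figures.** For the DLT row, prior beta(1,3), posterior P(rate > 0.25) = 1 − BetaCDF(0.25; 1+x, 3+n−x). At 2/3, 3/6, 4/9 and 5/12 this gives 0.831, 0.834, 0.842 and 0.852, against the printed 0.83, 0.83, 0.84 and 0.85. For the 6.9.6 rule, P(X ≥ 3 of 15) is 0.764 at 25% and 0.184 at 10%, against 0.76 and 0.18. The arithmetic is sound. What is open is which events are counted.

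**3. Effect on the count.** Let c be the rate of cardiac events that only 6.9.3 counts and b the DLT rate from other causes. Neither is given. I assume c from 0 to 10%, b = 5%, and independence, so p = 1 − (1−b)(1−c). The chance that at least one of 18 subjects has a different status is 1 − (1 − 0.95c)^18.

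| c | p | At least one of 18 differs | ≥3 of 15 | DLT row alone stops |
|---|---|---|---|---|
| 0 | 0.050 | 0 | 0.036 | 0.009 |
| 2% | 0.069 | 0.29 | 0.080 | 0.017 |
| 5% | 0.0975 | 0.58 | 0.175 | 0.037 |
| 10% | 0.145 | 0.83 | 0.374 | 0.090 |

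With b = 1%, the ≥3 of 15 column is 0.0004, 0.009, 0.056 and 0.220. One subject fewer at a DLT boundary lowers the posterior from 0.83–0.85 to 0.53–0.69.

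**4. Effect on stopping.** EF events already enter the asymptomatic cardiac row (1/3, 2/6, 3/9, 4/12). With 5% other DLTs, independent of EF events, the chance of stopping on either that row or the DLT row, without and with EF events counted as DLT, is 0.157 and 0.160 at a 5% EF event rate, and 0.305 and 0.310 at 10%. A grade 2 cardiac event that is not an EF event would enter only the DLT row; for those the last column above applies.

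**5. Scan timing.** Section 6.4.6 D allows 8 to 21 days between induction vaccines, so vaccine 6 falls on day 5×8 = 40 to 5×21 = 105. Two weeks later is week 54/7 = 7.7 to 119/7 = 17. Taking 3 months as 91 days, Booster 1 falls at week 131/7 = 18.7 to 196/7 = 28. The two time points are about 11 weeks apart. As illustration only: if half of EF events had reversed by Booster 1 (assumed), the asymptomatic row's stopping chance would fall from 0.150 to 0.075 at a 5% event rate, or from 0.299 to 0.150 at 10%.

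**The case against.** The governing list is largely identifiable: 6.7 D names Statistical Considerations, only one section has that title, and 6.9.3 defines DLT just before the rule that uses it. That stands as an inference. But the cross-reference is misnumbered, concerns the monitoring rule, and is followed by 6.7 D's own list.

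A reader might take the > signs literally and infer that 6.9.3 leaves grade 3 toxicity out of DLT. The documents do not support relying on that. The 6.9.3 list mirrors 6.7 D item by item, a strict reading would count grade 2 urticaria but not other grade 3 allergic reactions, and an underline is easily lost in PDF conversion.

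A reader might also infer that the week-8 scan is absent. Section 6.5 B permits it, since week 8 lies inside its window, and the optional repeat 1 month after vaccination suggests an earlier first scan. It is allowed but not fixed. The EOS LVEF is scheduled nowhere.

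Not every extra cardiac event would be a DLT, because 6.9.3 scores trastuzumab cardiac toxicity separately. So the rates in the working are rates of events attributed to vaccine.

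Finally, the true rate may be near zero. Section 5.3 describes earlier EF declines of about 10%, all above 50%, back at baseline on a 30-day repeat. As described, they do not meet the EF criteria. Those patients had not just had chemotherapy or trastuzumab, which limits the comfort. The 3-of-15 rule is itself offered only as an example. The fever limit in 6.7 D sits under the DLT heading, so it may be meant to apply to the list as well; even so, it is narrower than the 6.9.3 exemption.

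**Conclusion.** The point holds as an inconsistency that should be fixed. On the at-least reading, the sections differ on the cardiac threshold, the EF criteria, fever and the grading version, and no text says which applies. The week-8 LVEF is not fixed and the EOS LVEF is not scheduled, so part of the cardiac safety endpoint may go unmeasured.

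The effect is on the reported DLT count, possibly on the 3-of-15 judgement, and on the completeness of cardiac data. Its size is unknown and may be small: every probability above rests on assumed event rates, and no size is claimed for fever or for the grading version. It would be wrong to infer that the stopping rules are undermined. Combined stopping moves by 0.003 to 0.006 in the cases shown, and with fifteen subjects already enrolled at the first site, the looks at 3 to 12 are probably past. An EOS scan cannot change the DLT row, because 6.9.3 ties the DLT rate to the weekly vaccination schedule.

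**What to change.** 1. State that 6.9.3 governs DLT counting. Write ≥ for every grade limit now shown as > (other allergic, autoimmune, cardiac, hematologic and non-hematologic, leukapheresis), so that no grade 3 event counted by 6.7 D is lost except fever, as 6.9.3 provides. This uses the sponsor's own list and chooses no threshold after seeing data.
2. Replace the 6.7 D list with a cross-reference to 6.9. Keep the off-protocol sentence as a separate rule for the individual subject.
3. State that EF events attributed to trastuzumab enter the cardiac rows only, and that those attributed to vaccine also count as DLT. Section 6.9.5 assigns attribution only where possible, so say where an unattributed event goes.
4. Name CTCAE 4.03 in 6.7 B, 6.7 D, 6.7 E and 6.9.3.
5. In 6.5 B and Appendix 1, time the existing post-induction LVEF at 2 weeks after vaccine 6, and add the EOS LVEF that 6.9.3 already requires.
6. Re-score treated subjects. Report anyone whose DLT status differs under the 6.7 D list, including any fever case, and whether that alters the 3-of-15 judgement. List subjects without a week-8 or EOS LVEF.

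The cost is protocol wording, re-scoring of recorded events, moving one scan that is already scheduled, and one EOS LVEF per remaining subject.
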